### 6.2.3 Follow-up visits for TRACE RA participants

Patients are asked to attend visits at **3 months**, and then **6-monthly from randomisation**. When attendance is not possible the CRF may be completed by telephone interview, however, every effort will be made to have an actual attendance to clinic at least once a year - in many cases this may coincide with the patient's routine clinic visit appointment. If patients are to continue study treatment, preferably ALT (and if ALT not available then AST) measurements are mandatory within **6 weeks** of the follow-up visit - the overwhelming majority should be available through the patient's routine DMARD monitoring.

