### • Month 3 from first administration of trial drug

Every effort will be made to conduct this review appointment by clinic visit, but in exceptional circumstances it could be done by telephone interview. During this 3-month review appointment: (a) Actively seek whether muscle symptoms have occurred: **if** NEW and SIGNIFICANT muscle pain or weakness have occurred then measure contemporary ALT\*/AST and CK; (b) Record any serious adverse event (including any possible cardiovascular event - please see Appendix 5 for definition of cardiovascular event and Section 9 for detailed definitions of SAEs) and record length of any in-patient stay, whether for elective/planned procedures or not; (c) Review ALT/AST result: if ALT/AST available from within the last 6

weeks while patient was taking study treatment, other treatment was stable, and no new and significant muscle symptoms have been reported, then this value may be accepted and recorded in CRF with the date measurement was done; if ALT/AST not available within the last 6 weeks then request test and review result before advising patient whether they should / should not continue on study medication. (d) Record current relevant medication.

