### • 6- monthly from randomization

Follow-up may be conducted either by attendance at clinic or by telephone interview, but every effort will be made to have one clinic review appointment per year. During these 6-monthly reviews act as above (3-month review) but also record HAQ and EQ5D annually since randomisation.

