### In the presence of new and significant muscle symptoms:

(a) if CK>10xULN, then stop trial medication - not to be restarted.

(b) if ALT/AST<2xULNand CK<3xULN, trial medication can be continued with clinical follow-up. Further measurements of ALT/AST and CK can be requested if thought to be necessary by managing rheumatologist.

(c) if ALT/AST >2xULN and/or CK between 3-10xULN retest in 1-2 weeks: (c1) if normalisation has occurred to ALT/AST<2xULN and CK<3xULN then act as per option (b) above; (c2) if CK>10xULN stop trial medication; (c3) if ALT/AST>2xULN and CK again between 3-10xULN retest in 1 week: if elevation persists then stop trial medication.

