### 9.3 Adverse Events

An adverse event is the development of an undesirable medical condition or the deterioration of a pre-existing medical condition following or during exposure to a pharmaceutical product, whether or not considered causally related to the product. An undesirable medical condition can be symptoms (eg, nausea, chest pain), signs (eg, tachycardia, enlarged liver) or the abnormal results of an investigation (eg, laboratory findings, electrocardiogram).

Adverse events (either serious or non-serious) which lead to discontinuation of study treatment should be routinely recorded on the CRF. Other adverse events need not be recorded in the CRF.

In addition, new significant muscle symptoms should be sought at each study visit and recorded. If present AND if ALT is greater than the upper limit of normal then a blood CK should be measured (see section 6.2.3)

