### In the presence of new and significant muscle symptoms:

(a) If CK>10xULN, then stop trial medication - not to be restarted.

(b) If ALT/AST<2xULN and CK are <3xULN, trial medication can be continued with clinical follow-up. Further measurements of ALT/AST and CK can be requested if thought to be necessary by managing rheumatologist.

(c) If ALT/AST >2xULN and/or CK between 3-10xULN retest in 1-2 weeks: (c1) if normalisation has occurred to ALT/AST<2xULN and CK<3xULN then act as per option (b) above; (c2) if CK>10xULN stop trial medication; (c3) if ALT/AST>2xULN and CK again between 3-10xULN retest in 1 week: if elevation persists then stop trial medication.

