## APPENDIX 6: SAFETY OUTCOMES

Clinical laboratory safety parameters are shown below. Haematology and biochemistry will be performed at the local laboratories. All of the safety parameters are subject to routine regular monitoring for safety of the disease-modifying anti-rheumatic drugs (DMARDs). Such monitoring is required as part of routine clinical practice at intervals ranging between 2 weeks and 3 months for all but one DMARDs (the antimalarials). All patients will be questioned about muscle symptoms at each follow-up visit and if new and significant CK will be measured. Only serious adverse events will be recorded. Randomisation codes will be kept securely by participating pharmacists. If deemed necessary by the local investigator the randomisation code can be broken by contacting the local pharmacy.

Abnormalities of haematological and biochemical parameters in this population may be either due to DMARDs or the study drug. The decision of attribution will be left to the managing local investigator.

The study drug should be stopped if:

- Patient has new and significant muscle pains and CK>10xULN,Patient has new and significant muscle pains and ALT/AST >2xULN and CK between 3-10xULN and elevation persists upon retesting.
- Myopathy is diagnosed (muscle pain or weakness AND CK >10 times ULN)
- Elevation of CK to ≥5 times ULN, persisting on retesting 1 week later, should also lead to discontinuation of study medication.

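### Section 9.3 makes CK testing for new muscle symptoms depend on a raised ALT, contrary to section 6.2.3 and Appendix 6 and unworkable with the CK-based stopping rules

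*Protocol*

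**What the plan says.** Four places in the Protocol bear on when CK is measured and what is done with it.

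- **Section 9.3** has new significant muscle symptoms sought and recorded at every visit, and then says: "If present AND if ALT is greater than the upper limit of normal then a blood CK should be measured". The sentence ends with a pointer to section 6.2.3.
- **Section 6.2.3**, month 3 visit: if "NEW and SIGNIFICANT muscle pain or weakness have occurred then measure contemporary" ALT/AST and CK. The 6-monthly reviews are to follow the same steps. The section also lets AST stand in for ALT: "preferably ALT (and if ALT not available then AST) measurements are mandatory".
- **Appendix 6**: "All patients will be questioned about muscle symptoms at each follow-up visit and if new and significant CK will be measured". It adds a stop on CK alone, for a value of at least 5 x ULN "persisting on retesting 1 week later, should also lead to discontinuation of study medication".
- **Sections 6.2.3 and 11.2** give the same action rules for patients with new and significant muscle symptoms. Rule (a) in 6.2.3 is "if CK>10xULN, then stop trial medication - not to be restarted". Rule (b) in 11.2 is "If ALT/AST<2xULN and CK are <3xULN, trial medication can be continued with clinical follow-up". Rule (c) orders a retest if ALT/AST exceeds 2 x ULN, if CK is 3-10 x ULN, or both.

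Section 3.2 lists myopathy among the tertiary safety outcomes, defined by muscle symptoms together with CK above 10 x ULN. ALT plays no part in that definition.

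**The concern.** Section 9.3 sets two conditions for a CK test, whereas 6.2.3 and Appendix 6 set one. They disagree for one clearly defined patient: new significant muscle symptoms, with ALT at or below ULN. Section 9.3 does not call for CK in that patient; the other two do.

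The disagreement concerns a participant-safety check. The CK result decides whether trial medication is stopped for good, continued or paused for retesting, and it is the only laboratory criterion for myopathy. Section 2.2.1 gives concomitant muscle pathology as one reason why RA patients were kept out of the major statin trials, so muscle safety is one of the things this trial is meant to establish. A trigger that reads differently from section to section can be applied differently from site to site.

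**Working it through.** The trial has no figure to reproduce here. The check is a side-by-side reading.

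**Step 1. The trigger, for a patient with new significant muscle symptoms and ALT at or below ULN.**

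| Place | Condition for CK | CK called for? |
|---|---|---|
| Section 9.3 | Symptoms and ALT above ULN | No |
| Section 6.2.3, month 3 and 6-monthly | Symptoms alone | Yes |
| Appendix 6 | Symptoms alone | Yes |
| Section 11.2 | No explicit order; rules (a) to (c) presuppose a CK value | Implied |

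**Step 2. Does another test fill the gap?** CK is not in the baseline blood list of section 6.2.1 and not in the evaluations schema of Appendix 10. The symptom-triggered test is the only CK measurement that the visit schedule provides for.

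**Step 3. Can the action rules run without CK in this patient?**

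- Rule (a), permanent stop: depends on CK alone. It cannot be evaluated.
- Rule (b), continue: needs ALT/AST below 2 x ULN and CK below 3 x ULN. The ALT part is met; the CK part is unknown.
- Rule (c), retest: the ALT part is not met; the CK part is unknown.

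Stop, continue and retest all remain possible, and the protocol gives no basis for choosing. The further stop in Appendix 6, at 5 x ULN or more, also needs CK.

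**Step 4. The outcome.** Myopathy requires CK above 10 x ULN. Without a CK value this patient can neither be counted as a case nor ruled out as one.

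**Step 5. The pointer from 9.3 to 6.2.3.** Section 6.2.3 has no ALT condition, so the pointer leads to a different rule, and neither section says which governs. The 9.3 condition also names ALT only, although 6.2.3 accepts AST where ALT is unavailable.

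**Step 6. Once CK is measured, do the rules agree?** Take the same patient with ALT normal throughout and CK persistently between 5 and 10 x ULN.

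- In 6.2.3 and 11.2, the first result falls under (c), retest. At retest, (c1) fails because CK is not below 3 x ULN, (c2) fails because CK is not above 10 x ULN, and (c3) fails because it needs ALT/AST above 2 x ULN as well as CK of 3-10 x ULN. No branch leads to a stop.
- Appendix 6 stops study medication if CK of at least 5 x ULN persists at 1 week, with no ALT condition.

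Correcting 9.3 alone would therefore obtain the CK value but leave two different instructions on what to do with it.

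**The case against.** The strongest reply is that section 9.3 does not forbid CK at normal ALT and sends the reader to 6.2.3, where the visit procedure is set out in full. A site working from 6.2.3 or Appendix 6 will measure CK correctly. The harm needs a site that takes the 9.3 sentence at face value, and the protocol does not show that any site does. This stands, and it limits the conclusion to literal followers of 9.3. It does not remove the conflict, because the pointer carries no rule of precedence.

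It is also fair that section 11.2 never orders a CK test; its rules only imply one. The direct contradiction is with 6.2.3 and Appendix 6.

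A reader might try to put a number on the loss. Appendix 7 reports CK above 3 x ULN in 2.5% of atorvastatin patients in clinical trials. With 5342/2 = 2671 patients per arm, 0.025 x 2671 = 66.8, which suggests a range of 0 to about 67 patients missed. The documents do not support this as a bound:

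- It covers one arm, whereas in a double-blind trial the rule applies to both.
- The 2.5% comes from other trials of unstated duration, whereas follow-up here averages about 5 years (27000/5342 = 5.1 to 28000/5342 = 5.2).
- It is not restricted to patients with symptoms.
- Section 5 excludes patients with CK above 3 x ULN at entry, so the rate may not carry over.

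Two nearby wording points might be drawn in: the Appendix 6 statement restricting recording to serious adverse events, and the section 11.2 statement that atorvastatin has only two recognised adverse effects. Neither bears on the CK trigger. They are optional clean-up.

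**Conclusion.** The point holds. Section 9.3 contradicts 6.2.3 and Appendix 6 on when CK is measured, and it is incompatible with action rules that need CK at any ALT. The consequence is conditional: at a site that applies 9.3 literally, a symptomatic patient with ALT at or below ULN gets no CK, the CK-based stops cannot be applied, and myopathy is left undetermined.

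The size cannot be computed. The protocol gives no rate of muscle symptoms, no share of symptomatic patients with normal ALT, and no indication of which section sites follow. A reader might infer that CK has actually been withheld from patients or that the trial's efficacy conclusions are at risk. The protocol shows no evidence of the first, and nothing in this point touches the primary endpoint, sample size or primary analysis. It is a safety-monitoring inconsistency that bears on one tertiary outcome. It should be corrected because it concerns participant safety and the correction is simple.

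**What to change.** Replace the 9.3 sentence with: *If present, measure ALT (or AST) and CK, whatever the ALT or AST result (see section 6.2.3).*

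In the same edit, align rule (c3) in sections 6.2.3 and 11.2 with Appendix 6, for example by adding: *Whatever the ALT/AST, if CK is at least 5 x ULN and this persists on retesting at 1 week, stop trial medication.*

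The cost is wording changes in three sections at the next amendment and a few extra CK tests at sites that had followed 9.3. Sites already following 6.2.3 see no change in when CK is measured. The (c3) change asks for no stop beyond those Appendix 6 already requires.

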### 9.4 Serious Adverse Reactions (SAR)

**SERIOUS (as defined in Section 9.2)** adverse events, judged by the reporting investigator as having a reasonable causal relationship to atorvastatin, qualify as **serious adverse reactions**. This judgement of causality should be made without breaking the randomisation code – on the assumption that the patient has been exposed to atorvastatin.

SARs should be reported on the **serious adverse event report form** and faxed to the AR UK Epidemiology Unit **within 24 hours** of knowledge of the event.

[figure not shown]
### 9.5 Suspected Unexpected Serious Adverse Reactions (SUSARs)

For any reported SAR, the assessment of 'expectedness' will be made by the Chief Investigator (or their delegated deputy) based on the current Summary of Product Characteristics (SmPC)/Package Insert for atorvastatin. If confirmed as a SUSAR will be subject to expedited reporting by the trial sponsor (i.e. Chief Investigator and University of Manchester) to MHRA, therefore every effort should be made to notify the regional trials office within the timeframe shown below (Section 9.7). As a general rule, the treatment code for the specific patient should be broken before reporting a SUSAR to MHRA. Events associated with placebo will usually not satisfy the criteria for a SUSAR.

### 9.6 Reporting of SAEs, SARs and SUSARs to Pfizer

Although this is an investigator led clinical trial in which Pfizer (the Market Authorisation Holder for atorvastatin) is not acting as sponsor, there is a regulatory requirement that Pfizer be notified of all SAEs, SARs and SUSARs in a timely fashion. This reporting will be carried out by the co-ordinating centre at the University of Manchester and will be separately financed by Pfizer.

### 9.7 Recording and reporting of all SAE/SARs

### Flow diagram of SAE reporting and action taken following the report:

The patient should be followed-up until clinical recovery is complete and laboratory results have returned to normal, or until disease has stabilised. Information on final diagnosis and outcome of SAEs which may not be available at the time the SAE is initially reported should be forwarded on a copy of the SAE initial report form as soon as this information is available. Follow-up may continue after completion of protocol treatment if necessary.

All information regarding an SAE should be faxed to the University of Manchester on **[name]**, and information required by the drug manufacturer will be passed on by that trials unit. Centres are free to volunteer information to the drug manufacturer if they wish, but are under no obligation to do so.

### **10. STATISTICAL CONSIDERATIONS**

### 10.1 Sample size

The aim of the trial is to detect (with 80% power at the 5% significance level) a 32% relative risk reduction (RRR) in the primary endpoint attributable to treatment with atorvastatin and anticipating an average of 25% non-compliance. If the true effect of taking the treatment is a 32% RRR but only 75% of patients are compliant, then the effect seen in this trial should be about 24% (ie, 75% of 32%). The required number of first events (i.e. patients with events) to be able to detect such a reduction with 80% power at the 5% significance level is 434 (Appendix 8). The estimated average blinded event rate in all patients is expected to be 1.6-1.8% per annum. A maximum of around 27000 patient-years of follow-up is required for these event rates to produce the required number of first events (Appendix 8). Based on recruitment rates achieved between August 2007 and November 2010 and using a logarithmic decay model to reflect the decline in recruitment with time, it is estimated that 5342 patients recruited by March 2014 would provide between 27000 and 28000 patient-years of follow-up. If the blinded event rate is somewhat less than expected then the trial will continue (if necessary) until the required number of events has been accrued and all the available follow-up data will be used in the analysis.

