### 10.4 Planned analyses

All patients randomised will be included in the analysis, irrespective of whether the study drug is continued (ITT analysis). Cox regression models will be developed for time to occurrence of a first cardiovascular event or serious adverse event using treatment allocation as the independent variable.

The models will be adjusted for factors used in the stratification (centre) and for any baseline imbalances. However, the trial is of sufficient size to expect that most potential confounders (e.g. smoking, aspirin, NSAID/Coxib, corticosteroid, anti-TNF usage etc) are likely to be balanced between the groups. Treatment differences will be expressed as hazard ratios with 95% confidence intervals. Two-sided p values of  $\leq$ 0.05 will be considered significant.

Kaplan-Meier Product Limit (PL) estimates of the survival curves with 95% confidence intervals will be calculated.

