### 10.7 Interim analyses and its frequency

Interim analyses will be performed when the number of events reaches 25%, 50% and 75% of the total expected events. No formal stopping rule will be set but the DMC will advise the Chairman of the Trial Steering Committee that the trial should be stopped if, in DMC's view, the randomised comparison in the trial has provided both (a) proof beyond reasonable doubt that for all, or for some, types of patients the trial treatment is clearly indicated or clearly contraindicated in terms of a net difference in major morbidity and mortality, and/or (b) evidence that might reasonably be expected to influence the patient management of clinicians aware of the results of any other studies. Safety data will be continuously monitored by the independent DMC.

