### **APPENDIX 8: POWER CALCULATION AND OTHER STATISTICAL CONSIDERATIONS**

#### Table 1

Total number of patients with events and total number of events required for Cox regression (80% power at 5% significance level)

Reduction in Annual Event Rate

(after adjustment for non-compliance)	Number of patients with events	Number of events*
20%	631	671
21%	565	597
22%	509	534
23%	460	481
24%	417	434
25%	379	393
26%	346	358
27%	317	327
28%	291	299

\*assuming independence of events

#### Table 2

Expected total number of events for various combinations of annual event rate and patient-years of follow-up

	Patient-Years Follow-up						
Annual event rate*		1.3%	1.4%	1.5%	1.6%	1.7%	1.8%
	25000	325	350	375	400	425	450
	26000	338	364	390	416	442	468
	27000	351	378	405	432	459	486
	28000	364	392	420	448	476	504

\*overall event rate in the two groups combined

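### Section 10.1 gives 434 as the required number of patients with a first event; Appendix 8 gives 417, and 434 is its all-events figure

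*Protocol*

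**What the plan says.** Section 10.1 plans for "a 32% relative risk reduction (RRR) in the primary endpoint attributable to treatment with atorvastatin", diluted by 25% non-compliance to an observed reduction of about 24%. It then defines "The required number of first events (i.e. patients with events) to be able to detect such a reduction with 80% power" and puts that number at 434, referring to Appendix 8.

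Appendix 8, Table 1 is headed "Total number of patients with events and total number of events required for Cox regression" and has one column for each quantity. The 24% row reads 417 patients with events and 434 events. The events column is footnoted "assuming independence of events". Table 2 multiplies annual event rates by patient-years, and its heading speaks of a total number of events.

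Three other places use an event count:
- Section 10.4 specifies Cox regression on time to a first cardiovascular event.
- Section 6.4 lets the trial end at around 370 confirmed primary events, if that comes before March 2016.
- Section 10.7 says: "Interim analyses will be performed when the number of events reaches 25%, 50% and 75% of the total expected events". It does not say which total is meant, or whether events or patients are counted.

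**The concern.** Section 10.1 takes its number from one column of Table 1 and its label from the other. For a time-to-first-event Cox analysis, the information is the number of patients with a first event, so that is the count on which the 80% power rests. The protocol now gives two values for it, 434 in 10.1 and 417 in Table 1, and 6.4 works to a third figure of about 370.

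At stake is a clear event target. Follow-up, the end of the trial and the three interim looks all refer to a number of events. Patients stay in follow-up after an endpoint (6.4), and the composite contains both myocardial infarction and coronary revascularisation, so one patient can contribute more than one event. Whoever tracks events needs to know what is counted and up to what number.

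**Working it through.** **Inputs**
- Reduction seen in the trial: 0.75 × 32% = 24%, taken as hazard ratio 0.76 (10.1).
- Power and level: "to detect (with 80% power at the 5% significance level" (10.1).
- Two-sided testing: "Two-sided p values of" 0.05 or less are to count as significant (10.4).
- Patients: 5342 (10.1).
- Allocation 1:1. This is an assumption; the main text states no ratio.

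**Step 1: patients with events.** Schoenfeld: D = 4(1.960 + 0.842)² / (ln HR)². At HR 0.76, D = 31.40 / 0.0753 = 416.9, so 417.

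**Step 2: all events.** If events arise independently at a common rate, E = −N ln(1 − D/N). With N = 5342 and D = 417, E = 434.2.

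**Step 3: the same two formulas over the whole of Table 1.** Step 2 is applied to the printed number of patients.

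| Reduction | Patients, printed | Schoenfeld | Events, printed | Converted |
|---|---|---|---|---|
| 20% | 631 | 630.5 | 671 | 671.5 |
| 21% | 565 | 565.0 | 597 | 597.2 |
| 22% | 509 | 508.6 | 534 | 534.9 |
| 23% | 460 | 459.6 | 481 | 481.0 |
| 24% | 417 | 416.9 | 434 | 434.2 |
| 25% | 379 | 379.4 | 393 | 393.1 |
| 26% | 346 | 346.3 | 358 | 357.7 |
| 27% | 317 | 317.0 | 327 | 326.8 |
| 28% | 291 | 290.9 | 299 | 299.2 |

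Both columns are reproduced to within one in every row, so Table 1 is sound. Freedman's formula gives 423 in the 24% row and exceeds the printed patients column by 5 to 6 throughout, so a different formula does not explain 434.

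**Step 4: power at HR 0.76.** Power = Φ(½√D × |ln 0.76| − 1.960).
- D = 434: Φ(2.859 − 1.960) = 81.6%
- D = 417: 80.0%
- D = 370: Φ(2.639 − 1.960) = 75.2%

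**Step 5: patient-years at 1.6% per annum, if that is a first-event rate.** 417 / 0.016 = 26,063; 434 / 0.016 = 27,125. The difference is about 1,060.

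**Step 6: if 434 were counted as all events.** Under independence these are 5342 × (1 − exp(−434/5342)) = 416.8 patients, and power stays at 80%. If repeats cluster, it falls. The protocol gives no ratio of events to affected patients. Purely for illustration, assumed ratios of 1.1, 1.2 and 1.3 (Table 1 implies 434/417 = 1.04) leave 395, 362 and 334 first events, with power 77.8%, 74.2% and 70.8%.

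**Step 7: interim looks.** Using 434 in place of 417 moves the 25%, 50% and 75% looks by 17 × 0.25, 0.50 and 0.75, that is by about 4, 9 and 13 events.

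**The case against.** The strongest reply is that little harm follows. Section 10.1 names the correct unit. A team that follows it literally collects 434 patients with events and has slightly more power than planned. The planned 27,000 to 28,000 patient-years cover both 26,063 and 27,125. The interim looks hardly move, and 10.7 sets no formal stopping rule, so no boundary depends on the count. All of this stands.

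A reader might go further and infer that the target is in the wrong unit and the trial therefore underpowered. The documents do not support that. The loss in step 6 needs two things: a count of repeat events despite the definition in 10.1, and clustering of repeats within patients. The first is stated nowhere. The second is plausible, but the protocol gives nothing to size it.

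A reader might also take Table 2 as proof that the 1.6–1.8% rate includes repeats. Its heading speaks of a total, but its footnote describes a rate for the two groups combined, so total may only mean both arms together; and 10.1 treats the rate as producing first events. The unit is unclear, not shown to be wrong.

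What the reply does not remove is the misquotation itself, and the lack of any unit definition in 6.4 and 10.7.

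**Conclusion.** The point holds as an error of number: 10.1 should read 417 patients with a first event, and 434 belongs to the all-events column. This rests on the printed table and on a recalculation that assumes 1:1 allocation. Taken literally, the effect is conservative: 17 more patients with events than needed and 1.6 percentage points more power. A loss of power is conditional on how events are counted, and its size is unknown.

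The figure of around 370 in 6.4 is a separate and larger discrepancy. At HR 0.76 it gives 75.2% power even if all 370 are first events. Defining the unit in 6.4 without settling the number would leave the event target contradictory, so both belong in one correction.

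**What to change.** - **Section 10.1:** state 417 patients with a first primary event (Appendix 8, Table 1, 24% row), equivalent to about 434 events in all under independence.
- **Sections 6.4 and 10.7:** define the count as patients with a first confirmed primary event, and in 10.7 name the total to which the percentages apply.
- **Section 6.4:** reconcile around 370 with 417, or state the assumption under which 370 is sufficient.
- **Section 10.1 and Table 2:** say whether the 1.6–1.8% rate and the tabulated numbers count first events or all events.

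Table 1 is correct and need not change. The cost is an amendment of wording and a check that the blinded event tracker counts patients. No unblinded data are needed, and no study procedure changes.
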